5.4 MANAGEMENT OF EXTREME DATA ("OUTLIERS")

Before freezing the database, and prior to any statistical analysis, a review of the data will be performed to correct inconsistent and/or outlier data.

The agreements made will be validated by the sponsor and detailed in a data review report.

6 MODIFICATIONS TO THE ANALYSES PROVIDED FOR IN THE PROTOCOL

Not applicable

7 STATISTICAL ANALYSIS

7.1 STUDY POPULATION

7.1.1 Patient Status/General Study Data

Will be described:

- The number of participating centers in the study and the number of patients included per center
- The number of patients included
- The inclusion period (date of the first and last patient included)
- Duration of inclusion in months: (Date of last inclusion date of first inclusion+1) / 30.44
- Study duration in months: (Date of last patient follow-up date of first inclusion+1) / 30.44

An inclusion curve will also be presented.

7.1.2 Deviations from the protocol

Protocol deviations will be summarized in tables for all included patients, specifying for each type of deviation the number of patients concerned.

The minor/major nature of deviations will be defined with the Sponsor and reported in the data review report.

In the event of a major protocol deviation, patients will be excluded from the Per Protocol analysis population.

The list of deviations from the protocol will be given.

7.1.3 Populations of analysis

Analysis populations will be presented with the number of patients in each treatment group. Intent-to-treat (ITT) population: all included and randomized patients who used the pump device at least once.

Intent-to-treat (ITTm) population: ITT population with exclusion of the 4 patients discharged due to COVID-19.

Population Per Protocol (PP): ITT patients with no major protocol deviations.

Tolerance population: all patients who have used the pump device at least once.

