3.1.8 Randomization

Randomization will be performed using the eCRF provided to the investigators for the study. It will determine which arm the patient will be assigned to: either the "Omnipod" group (the patient will continue to use his current Omnipod pump) or the "Medtrum" group (the patient will have to switch to a Medtrum model).

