3.3 EXPECTED SERIOUS ADVERSE EVENTS

As with any Class IIB medical device, risks associated with use cannot be excluded.

Each patient will already be using an Omnipod® insulin pump at the time of inclusion in the study. The use of another pump model (CE marked and already used in other countries) does not present any additional potential risk.

Any serious adverse event, whether or not related to the device under study or its use, must be reported in accordance with the instructions in Chapter 13.

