11.2.2 Study populations

To meet the study objectives, 2 populations will be defined:

- ITT: all included patients who used the pump device at least once. Patients will be analyzed according to their group allocated by randomization.
- Per Protocol: ITT patients with no major protocol deviations.
- Tolerance population: all patients who have used the pump device at least once.

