4.3 INCLUSION OF PATIENTS

4.3.1 Inclusion criteria

To be included in the study, all patients had to meet all the following inclusion criteria:

- Patient with type 1 or type 2 diabetes, 18 years of age and older
- Patient already equipped with an Omnipod[®] insulin patch pump (Insulet) and a FreeStyleLibre sensor (Abbott)
- A1c between ≥6.5% ≤9.5%
- Treated with any type of rapid-acting insulin except FIASP (which can be substituted as needed) with up to 60 IU per day (no use of insulin supplements by pen injector allowed)
- Patient able to receive and understand study information, give written informed consent, and easily participate in the study

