 - The delivered insulin doses were obtained from the pump data record. The total volume and the distribution between basal and bolus as well as the evolution of these doses during the study will be observed.
 - Although not allowed in the study, possible additional insulin injections with a pen were documented when appropriate.

Source data	Bypass rule	Label	Format
Dates of inclusion	INC_D = (Date of last inclusion - date of first inclusion+1) / 30.44	Duration of inclusion (in months)	Digital
Inclusion and visit dates	STUDY_D = (Date of last patient follow-up - date of first inclusion+1) / 30.44	Duration of the study (in months)	Digital
Patient eligibility and randomization	ITT_D = -1 if the patient meets the inclusion and non- inclusion criteria and has used the pump device at least once -0 otherwise	Population ITT	0 = "No 1 = "Yes
ITT_D and major protocol deviation	PP_D = -1 if the patient belongs to the ITT population without major deviation from the protocol -0 otherwise	Population PP	0 = "No 1 = "Yes
Randomization	SAFT_D = -1 if the patient has used the pump device at least once -0 otherwise	Tolerance population	0 = "No 1 = "Yes
Pre-inclusion date and date of birth	AGE_D = (Pre-Entry Date - Date of Birth) / 365.25	Age (in years)	Digital
Date of pre- inclusion and date of discovery of diabetes	DIAB_D = (Pre-inclusion date - date of discovery of diabetes) / 365.25	Time since discovery of diabetes (in years)	Digital
Time since discovery of diabetes (in years)	DIAB_3CL = -0 if DIAB_D <5 -1 if DIAB_D = [5 ; 10[-2 if DIAB_D = >10	Time since discovery of diabetes (in classes)	0 = "Less than 5 years 1 = "Between 5 and 10 years

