7.4.2 Secondary endpoint analyses

Analyses will be performed on the ITTm population.

Each variable will be described globally and by pump group.

The secondary endpoints are:

1. HbA1c

The evolution of HbA1c (measured in the laboratory) between D0 and 3M will be described, and a comparison between the groups will be made using a Student's t test or a Mann and Whitney test.

2. Glucose level measurement

The mean blood glucose level and its standard deviation (Blood Glucose Deviation SD) will be described over each period (between V1 and V2, then between V2 and v3, then between V3 and V4) and over the total duration of the study (mean, median, standard deviation, Q1-Q3, minimum and maximum). The coefficient of variation of glucose values will also be described.

The evolution of the average blood glucose level compared to baseline will be described at each visit.

FSL wear time (%) will be described.

The % of blood glucose values spent in target (time in range: [70; 180]), hypoglycemia (<70mg/dl), and hyperglycemia (>180 mg/dl) will be described over each time period in each pump group and in the total population.

For these criteria, comparisons between groups will be made using the Student or Mann-Whitney test.

3. Glycemic events

The number of hypoglycemic events will be described overall and in each period by severity level (according to ADA consensus definitions) overall and in each pump group.

Comparisons between groups will be made using Student or Mann-Whitney tests.

The % of time spent in hyperglycemia will be described overall and over each period and in each pump group. Comparisons between groups will be made using Student's t test or Mann and Whitney test.

4. Device tolerance

The analysis of this criterion is detailed in section 7.4 of this document.

5. Incidents with devices

The following criteria will be described for each period and by pump group (after reclassification):

- Pump occlusion (yes; no)
 - If yes, number of times
- Pump detachment (yes; no)
 - If yes, number of times
- Complete stop / breakage of the pump (yes; no)
 - If yes, number of times
- Other pump malfunction (yes; no)
 - All other possible malfunctions will be listed.

6. Patient satisfaction

The following criteria will be described for each period and by pump group:

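### The SAP defines ITT in two ways, and if the condition of pump use means the allocated pump, it can in practice exclude only Medtrum-arm patients

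*SAP*

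**What the plan says.** The ITT population is described in three places.

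- Protocol 11.2.2: "ITT: all included patients who used the pump device at least once", analysed by allocated group.
- SAP 7.1.3: "all included and randomized patients who used the pump device at least once".
- SAP 4.4.3, derived-variable table: ITT_D equals 1 "if the patient meets the inclusion and non- inclusion criteria and has used the pump device at least once", and 0 otherwise.

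SAP 7.1.3 builds two further sets from ITT. PP is ITT without major deviations, and ITTm is ITT without the 4 patients discharged because of COVID-19. Under SAP 7.4.1 the primary analysis uses PP. The sensitivity analysis uses ITTm, with missing values replaced by the mean or median. For the secondary endpoints SAP 7.4.2 states: "Analyses will be performed on the ITTm population". Tolerance is the exception and has its own population.

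On pump use, Protocol 3.3 states: "Each patient will already be using an Omnipod® insulin pump at the time of inclusion in the study". In the Omnipod group, according to Protocol 3.1.8, "the patient will continue to use his current Omnipod pump", while a patient in the Medtrum group has to change to the new model. The trial is open-label (Protocol 2.1, SAP 4.1).

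**The concern.** There are two separate problems.

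First, the definition in the text and the rule to be programmed differ. A randomised patient later found ineligible is in ITT under SAP 7.1.3 and out of it under ITT_D. Both documents foresee such patients: Protocol 6.4 lists a non-compliant inclusion as a ground for withdrawal, and SAP 7.2 lists failure to meet the criteria among the reasons for not completing. SAP 10 requires double programming of the populations and cites 7.1.3, so programmers working from different sections could produce different flags.

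Second, the use condition depends on behaviour after an open-label allocation, and the two arms do not face it equally. One arm has only to continue; the other has to start something new. If patients who decline or fail to start differ in glycaemic control, leaving them out of one arm selects that arm. The ITT-type analysis is supposed to check the PP result (Protocol 11.2.1). It checks less well if it omits, in one arm only, patients whom PP may also omit.

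**Working it through.** **The plan's own figures.** With one-sided alpha 2.5%, power 80%, true difference 0 and margin 0.4 (SAP 5.1), n per group = 2 × SD² × (1.960 + 0.842)² / 0.4².

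- SD 0.55: 2 × 0.3025 × 7.85 / 0.16 = 29.7, so 30 per group and 60 in total; 60 / 0.8 = 75 randomised.
- SD 0.8: 2 × 0.64 × 7.85 / 0.16 = 62.8, so 63 per group and 126 in total.

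Both match the SAP. They supply the scale used below.

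**Definitions side by side.**

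| Source | Use condition | Eligibility condition |
|---|---|---|
| Protocol 11.2.2 | yes | not stated |
| SAP 7.1.3 | yes | not stated |
| SAP 4.4.3, ITT_D | yes | yes |

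SAP 6 records no change from the protocol analyses, although the eligibility condition in ITT_D is absent from Protocol 11.2.2.

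**What the use condition can remove.** The documents do not say which pump is meant, or from when use counts.

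| Reading of the pump device | Omnipod arm | Medtrum arm |
|---|---|---|
| Any pump, including use before randomisation | nobody | nobody |
| Allocated pump, after randomisation | in practice nobody, since patients continue | those who never start |
| Medtrum pump only | everyone in the comparative phase | those who never start |

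The third reading is unworkable, because ITT must contain both arms. The first makes the condition redundant. The second is the natural one, and there the effect is confined in practice to one arm.

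**Size of the shift.** If a fraction p of an arm has a mean g away from the rest, excluding it moves the arm mean by p × g. The documents give neither p nor g, so both are assumed, with 50 per arm from the 100 patients included.

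- 2 non-starters, g = 0.3: 0.04 × 0.3 = 0.012, or 3% of the margin.
- 5 non-starters, g = 0.5: 0.10 × 0.5 = 0.05, or 12.5% of the margin.
- Wider range: 1 non-starter with g = 0.2 gives 0.02 × 0.2 = 0.004; 5 with g = 0.8 give 0.10 × 0.8 = 0.08, or 20% of the margin.

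The unadjusted standard error is 0.8 × √(1/50 + 1/50) = 0.16, so a shift of 0.05 is about 0.3 standard errors. The sign depends on whether non-starters are worse or better controlled.

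**Loss of precision.** Power with 50 against 50 is Φ(0.4/0.16 − 1.96) = Φ(0.54) = 70.5%. With 50 against 45 the standard error is 0.164 and power is 68.2%. The cost is small.

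**Would adding non-starters and imputing them help?** Suppose 5 of 50 Medtrum patients are imputed. With their own arm's mean, the unadjusted arm mean does not move. With the pooled mean of 45 Medtrum and 50 Omnipod values, the Medtrum mean moves towards Omnipod by 0.10 × 50/95 = 0.053 of the observed difference, so the difference shrinks by about 5%. Neither recovers the non-starters' outcomes, and both understate the variance. Only observed data remove the selection. The primary endpoint comes from the patient's own FreeStyle Libre (Protocol 10.1), whichever pump is worn, so such data can exist.

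**The case against.** The strongest reply is that no harm is shown. The documents report no non-starters. Randomisation, training and supply of the Medtrum equipment all belong to the inclusion visit (Protocol summary and 7.2), so there is little time in which to drop out before first use. The recruitment worry in Protocol 2.1 concerns the other arm: controls are offered a month on the Medtrum pump as an incentive. A used-at-least-once rule is a familiar modified-ITT convention. SAP 7.1.3 presents population counts by group, so an imbalance would show. The primary model adjusts for baseline estimated HbA1c, which would absorb much of any gap already present at entry. All of this stands, and it limits the likely size.

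It may also be said that the two definitions coincide, because SAP 4.2.1 allows inclusion only of patients who meet the criteria. Protocol 6.4 foresees inclusions later found non-compliant, so included and eligible are not the same, and the conflict remains.

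Three stronger readings are tempting but unsupported.

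- A reader might infer that the rule excludes no Omnipod patient by construction, since all used an Omnipod before randomisation. If earlier use counts, every Medtrum-arm patient qualifies too and nobody is removed. The asymmetry needs the allocated-pump reading, and then holds in practice rather than by logic.
- A reader might infer that the primary PP result is compromised. PP may drop non-starters in any case as major deviations, a classification that SAP 7.1.2 leaves to the data review.
- A reader might count the eligibility condition as part of the one-sided effect. It can act in both arms.

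**Conclusion.** The point holds in limited form. That SAP 7.1.3 and ITT_D disagree is plain from the text and does not depend on how many patients started the pump. The one-arm effect of the use condition holds if the pump device means the allocated pump, which is the natural but unstated reading. It matters for ITTm, and so for the sensitivity analysis of the primary endpoint and the secondary comparisons other than tolerance.

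The likely size is small: 0.012 to 0.05 points on the assumed inputs and 0.08 at the edge of the wider range, before baseline adjustment, against a margin of 0.4. The direction is unknown. The documents do not support a claim that the conclusion on non-inferiority would change. The reason to act is that the check on PP should not depend on behaviour after allocation, and the correction costs little.

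**What to change.** - In Protocol 11.2.2 and SAP 7.1.3, define ITT as all randomised patients, analysed as allocated. Note the change in SAP 6.
- In SAP 4.4.3, remove the eligibility and use conditions from ITT_D so that it matches, and let ITTm follow from the new ITT.
- State that observed FreeStyle Libre data from non-starters who remain in follow-up are used and not replaced by imputed values.
- Report the number who never started the allocated pump, by arm.
- Keep the use condition for the tolerance population only, and define the pump device there: which pump, and from when use counts.
- Never starting the allocated pump may remain a major deviation for PP.

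The cost is a few sentences, one line of the derivation and one table row. The downside is that a few patients with missing outcomes, or still on Omnipod, enter the ITT-based sets, which may slightly dilute a difference. In a non-inferiority trial that is a reason to keep PP as the primary analysis alongside, not to narrow ITT.

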7.2 END OF STUDY

Will be described:

- Patient who completed the study according to the protocol
 - If not, reason:
 - Non-compliance with the criteria (screen failure)
 - Malfunction of a medical device that does not allow the study to continue
 - Patient's decision
 - Investigator's decision
 - Lost to view
 - Other
 - Other reasons will be given in a listing

7.3 PATIENT CHARACTERISTICS AT INCLUSION

Inclusion parameters will be described globally and according to their group allocated by randomization on the **ITT population and then on the ITTm population**. Only demographic data will be described for **patients discharged with COVID-19**. Demographics

- Age (years)
- Gender (female; male)
- Type of diabetes (type 1; type 2)
- Time since the discovery of diabetes
- Time since discovery of diabetes (<5 years; 5-10 years; >10 years)

- Type of diabetes treatment:
 - Time since starting pump therapy (months)

Associated oral treatment

- For patients with type 2 diabetes:
 - Associated oral treatment (yes; no)
 - The list of associated oral treatments will be given via a listing

Clinical examination

- Weight (kg)
- Size (cm)
- BMI calculated (kg/m²)
- BMI calculated in classes (Lean: <18.5 kg/m²; Normal: 18.5-<25 kg/m²; Overweight: 25-<30 kg/m²; Obese: >= 30 kg/m²)
- Heart rate (bpm)
- Systolic blood pressure (mmHg)
- Diastolic blood pressure (mmHg)

Biological data

• Last HbA1c measurement in the laboratory (%)

Sensor data

- Estimated HbA1c (FSL) (%)
- FSL Wear Time (%)
- FSL wear time > 70% (yes; no)
- Average blood glucose (FSL) (mg/dl)
- Blood glucose SD (FSL) (mg/dl)
- Coefficient of variation of glucose values (%)
- Number of hypoglycemia
- Time spent in hypoglycemia <70 mg/dl (%)
- of normoglycemic values > 70-180 mg/dl (%)
- Time spent above >180 mg/dl (%)

Pump data

- Name of insulin used (Novorapid; Humalog; Apidra; Other)
 - If other, details will be given in a listing
- Average total daily insulin dose:
 - Average Daily Basal Dose
 - Average daily bolus dose
 - Number of Boluses/day

7.4 ANALYSIS OF THE EVALUATION CRITERIA

7.4.1 Primary endpoint analysis

The primary endpoint is the estimate of HbA1c at 3 months based on the mean of continuous glucose measurements obtained during the last 10 weeks of follow-up.

HbA1c estimation will be described by treatment group and then by type of diabetes.

The non-inferiority analysis of the primary efficacy endpoint will be performed with an ANCOVA, with the medical device as an explanatory variable and an adjustment on the estimate of HbA1c at Baseline, on the PP population.

If the upper bound of the IC95% of the Omnipod-Medtrum estimated difference in means (LSmeans) exceeds the non-inferiority bound set at 0.4, non-inferiority will not be demonstrated.

If non-inferiority is demonstrated, a superiority analysis will be conducted. If the upper bound of the IC95% of the estimated difference in mean is less than -0.3, superiority will be demonstrated.

The MIXED procedure (SAS® 9.4) will be used.

Code:

```
proc mixed data=XX order=data;
where PP = 1;
class DM;
model ESTIM_HBA1c = ESTIM_HBA1c_BASELINE DM;
lsmeans DM / diff=control cl;
run;
```

A sensitivity analysis will be performed on the ITTm population with imputation of missing data by the mean or median according to the distribution of the primary endpoint.

A subgroup analysis will be performed on the population of patients with an LSP wear rate >70% at M3.

Exploratory analysis:

Univariate analyses will be conducted on age in 2 classes (below or above the median), sex, type of diabetes, center, and duration of diabetes in 3 classes (<5 years; between 5 and 10 years; >10 years). If the p-value <0.05, the variable will be included in the full model. Then a top-down stepwise strategy will be conducted to select the variables for the final model.

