Statistical analysis	
Data processing and statistical analysis will be carried out by the service provider, Axonal-Biostatem.
 
The statistical analyses will be described in a Statistical Analysis Plan (SAP) validated by the Sponsor and the Scientific Committee, prior to the freeze-in.
 
Statistical analyses will be performed after baseline freezing of the data with SAS® software (SAS Institute, NC, Cary, USA), version 9.4 or later.
 
Demographic and efficacy/performance analyses will be performed in the ITT population. The primary endpoint will be analyzed in PP (Per Protocol) and then validated in the ITT (intention to treat) population. The safety analyses will be performed in the safety population.
 
For quantitative variables, the usual statistics (n, missing n, mean, standard deviation (SD), median, first and third quartiles (Q1 and Q3), minimum and maximum) will be presented. IC95% may be

	
presented if relevant (especially for the primary endpoint).
 
For categorical variables, the usual statistics (n, missing n, frequency and percentage) for each modality will be provided.
 
Descriptive statistics will be provided in aggregate and by pump group.
 
The type 1 error, α, is set at 5% when the tests used will be two-sided (superiority) and α will be set at 2.5% when the tests will be one-sided in the case of Noninferiority (IC95%).
 
Analysis of the main objective
 
The non-inferiority analysis will be produced via an Ancova or mixed model on the Per-Protocol population and then on an intention-to-treat basis.
 
If non-inferiority is demonstrated, a superiority analysis will be conducted.
 
Analysis of secondary objectives
 
The secondary criteria will be described and then be the subject of mixed or Ancova models.
 
A non-inferiority analysis on HbA1c data and superiority analyses on Time in range, number of glycemic events, patient satisfaction will be performed.

Regulatory framework	ID-RCB number, CPP opinion, CNIL MR001 and RGPD compliance, information to the ANSM, approval of investigator contracts by the CNOM, transparency obligations
Logistics	CRO Axonal-Biostatem (Nanterre, France)

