11.2 STATISTICAL ANALYSIS

11.2.1 *General statistical methods*

Data processing and statistical analysis will be carried out by the service provider, Axonal-Biostatem.

The statistical analyses will be described in a Statistical Analysis Plan (SAP) validated by the Sponsor and the Scientific Committee, prior to the freeze-in.

Statistical analyses will be performed after baseline freezing of the data with SAS® software (SAS Institute, NC, Cary, USA), version 9.4 or later.

Demographic data analyses will be performed in the ITT. Safety analyses will be performed in the Tolerance population. Non-inferiority analyses will be performed in the Per Protocol population and validated in the ITT population.

For quantitative variables, the usual statistics (n, missing n, mean, standard deviation (SD), median, first and third quartiles (Q1 and Q3), minimum and maximum) will be presented.

IC95% may be presented if relevant (especially for the primary endpoint).

For categorical variables, the usual statistics (n, missing n, frequency and percentage) of each modality will be provided.

Descriptive statistics will be provided in aggregate.

The type 1 error, α , is set at 5% for all analyses.

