11.2.4 Analysis of the effectiveness / performance of the device

Analysis of primary efficacy endpoint:

The non-inferiority analysis of the primary efficacy endpoint will be performed with an ANOVA, with the DM as an explanatory variable, on the *per protocol* population and then on the *intention-to-treat* population. If the upper bound of the IC95% of the Omnipod-Medtrum estimated difference in means (LSmeans) exceeds the non-inferiority bound, it will be rejected.

Non-inferiority bounds are defined in this protocol and will be used in the statistical analysis plan.

If non-inferiority is demonstrated, a superiority analysis will be conducted.

Secondary efficacy endpoint analyses:

The secondary efficacy endpoints will be analyzed for the variables listed below.

Each variable will be described globally and by pump group.

In case of non-inferiority analysis, the same methodology as for the primary endpoint will be used.

In case of comparison of quantitative variables, parametric (T-test) or non-parametric (Mann-Whitney) tests of comparison of means will be used. In case of comparison of qualitative variables, CHI² or Fisher exact tests will be used.

In case of tests on changes within each group, paired data tests will be used (paired data T-test or Wilcoxon signed ranks test, depending on the distribution of the data).

❖ **HbA1c:**

- Evolution of the value measured in the laboratory from a blood sample taken before the D0 visit and just before the 3-month visit
- Description in the total population, in each group and comparison between groups.

❖ **Glucose measurements**

- Average of glucose measurements over each period and over the entire study duration
- Description of the minimum and maximum values over the total duration of the study
- Description of the % of Time in Range (see ADA and International Consensus on Time in Range recommendations^{25,26})
- Description in the total population, in each group and comparison between groups.

❖ **Glycemic events**

- Description of the number of symptomatic and non-symptomatic hypoglycemic events during the evaluation period, broken down by severity level (see ADA consensus definitions²⁵)
- Description of the number of symptomatic and non-symptomatic hyperglycemia events during the evaluation period, broken down by severity level (see ADA consensus definitions²⁵)
- Description in the total population, in each group and comparison between groups.
-

❖ **Device tolerance**

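### The SAP decides non-inferiority on the per-protocol set alone, replaces the protocol's ITT validation with a sensitivity analysis that has no stated role and uses mean or median filling, and declares no change

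*SAP*

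**What the plan says.** **Protocol.** ITT follows PP for the primary endpoint in three places.
- Summary, Statistical analysis: "The primary endpoint will be analyzed in PP (Per Protocol) and then validated in the ITT (intention to treat) population". The same paragraph adds: "Demographic and efficacy/performance analyses will be performed in the ITT population".
- Section 11.2.1: "Non-inferiority analyses will be performed in the Per Protocol population and validated in the ITT population".
- Section 11.2.4: the non-inferiority analysis is run "on the *per protocol* population and then on the *intention-to-treat* population".

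Section 11.2.2 defines ITT, PP and a tolerance population. It has no ITTm.

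**SAP.** Section 7.4.1 fits the ANCOVA with "an adjustment on the estimate of HbA1c at Baseline, on the PP population". The code restricts to `where PP = 1`, and the non-inferiority and superiority rules are attached to that model. The only other analysis of the whole comparison is this: "A sensitivity analysis will be performed on the ITTm population with imputation of missing data by the mean or median", the choice depending on the distribution of the endpoint. Section 7.1.3 defines ITTm as ITT without the 4 patients discharged because of COVID-19. Section 7.4.2 puts the secondary endpoints on ITTm. ITT itself is used only to describe baseline (7.3). Section 6, headed "MODIFICATIONS TO THE ANALYSES PROVIDED FOR IN THE PROTOCOL", is filled in as not applicable.

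**Who is in PP.** Neither document lists the major deviations. SAP 7.1.2: "The minor/major nature of deviations will be defined with the Sponsor and reported in the data review report".

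**The concern.** The ITT step guards against a claim that depends on who was left out. That matters here because the trial is open-label, only the Medtrum arm changes device (Protocol 3.1.8), and the major deviations that define PP are classified with the sponsor. ITTm still contains deviators who have data, so it could serve as a check, but the SAP does not say what follows if it fails. A PP pass with an ITTm failure would still be reported as non-inferiority.

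The supporting analysis also uses a poor method. Filling missing outcomes with one value makes non-inferiority easier to show in that analysis, whether the value is pooled or by arm, and the SAP does not say which. SAP 5.3 covers only dates and negative durations, so nothing else governs missing outcomes.

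A smaller wording conflict adds to this. The derived variable ITT_D (SAP, derived criteria) requires that eligibility criteria be met; SAP 7.1.3 and Protocol 11.2.2 do not state this. Both documents define inclusion by eligibility, but Protocol 6.4 foresees inclusions later found non-compliant, and their place in ITT is unclear.

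**Working it through.** **1. The texts side by side**

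| Item | Protocol | SAP |
|---|---|---|
| Deciding analysis | PP, then ITT (Summary, 11.2.1, 11.2.4) | PP only, in text and code (7.4.1) |
| Second analysis | ITT validation | ITTm sensitivity, no decision role (7.4.1) |
| Secondary efficacy | ITT (Summary) | ITTm (7.4.2) |
| Declared change | – | None (6) |

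**2. The plan's own figures.** Margin 0.4, true difference 0, one-sided 2.5%, power 80%, 1:1: n per group = 2(1.960 + 0.842)² × SD² / 0.4².
- SD 0.55: 29.7, so 30 per group; 60/0.8 = 75 randomised. Matches.
- SD 0.8 (SAP 5.1): 62.8, so 63 per group, 126 in total. Matches.

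No sample-size figure is wrong on this point.

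**3. Mean filling, for the ITTm analysis taken alone.** Assumed: 48 per arm (100 included less 4, equal split), SD 0.8, true difference 0.4, outcomes missing at random at rate m, baseline correlation 0-0.8. The documents give neither m nor the correlation. The 20% in SAP 5.1 also covers major discrepancies, so it is an upper limit for m.
- *By arm.* The residual variance is shrunk by about (1 − m), and the model counts n patients where n(1 − m) were observed. Model SE / true SE ≈ √(1 − m) × √(1 − m) = 1 − m, so 0.90 at 10% and 0.80 at 20%. Simulation: 0.89-0.90 and 0.77-0.79. Error ≈ Φ(−1.96 × 0.9) = 3.9% and Φ(−1.96 × 0.8) = 5.8%. Simulation: 3.8-4.0% and 5.9-6.3%.
- *Pooled.* The SE is about right (ratio 0.99-1.01), but the difference shrinks by (1 − m): 0.4 × 0.9 = 0.36 and 0.4 × 0.8 = 0.32. Simulated error: 4.5-5.8% and 8.3-11.8%.

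Only mean filling was simulated, not median. With complete cases standing in for PP, the error under random loss is 2.3-2.6%.

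**4. What a both-must-pass rule would add (illustration).** Same assumptions. Suppose 5 Medtrum and 0 Omnipod patients, all with data, are excluded from PP and are 0.4 worse than other Medtrum patients, with the overall difference held at 0.4.
- PP difference = 0.4 − 0.4 × 5/48 = 0.358, a shift of 0.0417.
- Correlation 0: SE = 0.8 × √(1/43 + 1/48) = 0.168; error = Φ(−1.96 + 0.0417/0.168) = 4.3%.
- Correlation 0.8: SE = 0.168 × √(1 − 0.64) = 0.101; error = Φ(−1.96 + 0.0417/0.101) = 6.1%.
- Simulated: PP alone 4.3-6.0%; PP and full set both passing 2.2-2.4%.
- If 5 and 5 are excluded, all 0.4 worse, the shifts cancel and PP stays at about 2.5%.
- If the 5 Medtrum deviators are no worse, PP is 2.3-2.6%.

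**5. Patients who leave without an outcome (5 vs 0, 0.4 worse).** If V2 shows nothing: PP 4.3-6.1%; also requiring ITTm 4.3-5.5%; also requiring multiple imputation on baseline and V2 4.0-5.3%; with +0.4 added to imputed Medtrum values 2.3-2.5%. If V2 already shows the worsening (correlation 0.4-0.8): PP 4.6-6.2%, with ITTm 4.3-5.6%, with multiple imputation 2.6-3.0%. V2 was assumed observed for everyone, which a patient leaving before week 4 would not satisfy.

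**The case against.** **ITTm is close to ITT and is not hidden.** It is defined in SAP 7.1.3, baseline is described on both sets, and demographics are given for the COVID-19 patients. This is true, but section 6 still declares no change, and a sensitivity analysis with no rule is not a validation step.

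**The error rates in step 4 do not measure the swap of ITT for ITTm.** This stands. The simulated full set has the size of ITTm and nothing is imputed, so the figures measure a both-must-pass rule. The effect of removing the 4 COVID-19 patients has not been quantified. The inflation also comes from an assumed imbalance between arms, for which the documents give no figure.

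**Device malfunction as a reason for leaving (Protocol 6.4) mostly produces missing outcomes, not deviators with data.** This also stands. Step 5 shows that requiring ITT then helps little unless V2 shows the worsening.

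**PP is not chosen after seeing results.** SAP 5.4 places the data review and its report before database freeze and before any analysis. That limits selection, though it does not blind an open-label trial. The protocol lists no major deviations either, so that gap is not new in the SAP.

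**The protocol never defines validation.** A reader might infer that it already requires both sets to pass. It does not say so; that rule is one reading.

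**Conclusion.** The departure is real and should be corrected: the primary claim is decided on PP alone, the protocol's ITT analysis is gone, and section 6 is wrong to declare no change. This rests on the text and needs no simulation. The practical consequence is that a failing ITTm would not stop a non-inferiority claim.

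Mean or median filling is a wrong method for the supporting analysis. Its own one-sided error would be about 4-6% at 10% missing and 6-12% at 20%, under the assumed missing rates and correlations.

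Two stronger readings are tempting and not supported. One is that the trial's false-claim rate is 4-12%: the filling does not enter the PP model, and under random loss it does not inflate the PP-based claim. The other is that dropping ITT has been shown to inflate the error: PP alone reaches about 4-6% only if worse-performing deviators with data fall mainly in the Medtrum arm, and it stays near 2.5% if exclusions are balanced.

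**What to change.** In SAP 7.4.1, restore the ITT analysis of the primary endpoint with the same ANCOVA, the 0.4 margin and the difference written as Medtrum minus Omnipod (as in SAP 5.1). State its role. Preferred wording: *Non-inferiority is concluded only if the upper bound of the two-sided 95% CI of Medtrum minus Omnipod is below 0.4 in both PP and ITT.* If the sponsor does not want this, declare and justify the change in section 6.

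Replace mean or median filling with multiple imputation by arm, or a likelihood-based model, using baseline and any available V2 estimated HbA1c (collected under Protocol 7.4). Add a non-decisive check that adds +0.4 to imputed Medtrum values. Keep ITTm as supplementary, and declare it and its use for the secondary endpoints in section 6. Align ITT_D with SAP 7.1.3 and Protocol 11.2.2, and say how inclusions later found non-compliant are handled.

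The cost is SAP wording, one imputation program and a slightly stricter claim; no new data. Power at a true difference of 0, 48 per arm, SD 0.8:

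| Correlation | PP alone | PP and ITT, 10% missing, multiple imputation | PP and ITT, 10% deviators with data |
|---|---|---|---|
| 0 | 62.7% | 60.2% | 59.7% |
| 0.4 | 70.6% | 68.1% | 68.1% |
| 0.6 | 81.3% | 79.3% | 79.6% |
| 0.8 | 96.6% | 96.2% | 96.4% |

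The loss is 0.2-3.0 points. Making the +0.4 check decisive would cost 4-11 points, so it should stay non-decisive.
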